Study Protocol and Statistical Analysis Plan

Culturally Tailoring an Advance Care Planning Intervention for American Indians

ID: 1685879-1

June 30, 2024

Study Aims

This project had three specific aims: 1. Culturally tailor the content of the Make Your Wishes About You (MY WAY) ACP curriculum and guide for one American Indian Tribe; 2. Assess the feasibility of the culturally tailored MY WAY ACP curriculum and patient education guide with the tribe; and 3. Examine the preliminary outcomes of the culturally tailored MY WAY ACP curriculum guide with 70 tribal members.

Study Protocol

Study Design

We used a quasi-experimental waitlist-controlled study design to test the hypothesis that after participating in the tailored MY WAY intervention, participants would experience decreased ACP barriers and increased ACP facilitators, readiness, self-efficacy, and completion. This design split our total participant pool into two cohorts to allow for a comparison group while still providing the intervention to all participants. Cohort 1 received the intervention immediately after study enrollment and served as the intervention group. Results from Cohort 1 were then compared to the waitlisted cohort, or Cohort 2, who waited over 3 months on average to receive the intervention.

Intervention

The intervention consisted of two steps: attendance at a Community Information Session (CIS) and attendance at an individual Sharing Session (SS).

Recruitment

Study eligibility criteria included being an enrolled Tribal member, spouse of a Tribal member, first descendant, or a member of another AIAN Tribe, aged ≥ 18 years, and residing within the Tribal service area. We recruited potential participants using convenience sampling

techniques. We made in-person study recruitment announcements at 13 Tribal venues and left flyers and hung posters at 26 locations. We also ran an ad in the Tribal newspaper and on three billboards. Tribal programs distributed MY WAY information on our behalf via their social media and/or email listserv. We also developed a project website and ran a short video on the local Tribal television station. Interested people were directed to call the Project Coordinator by telephone and/or speak with staff at a CIS and then screened for study eligibility and enrolled, if eligible.

Data Collection

All study participants completed informed consent documents before study participation and all who completed the full intervention and the interviewer-administered surveys received \$85 in gift card incentives. Data were collected via surveys from Cohort 1 immediately before the CIS (“intervention baseline survey”), 8-9-weeks after the CIS at posttest (“post-program survey”), and 6-month follow up (“follow-up survey”). For Cohort 2, survey data was collected at baseline (“control baseline survey”), an average of 13 weeks immediately before CIS attendance (“intervention baseline survey”), and an average of 12-weeks after the CIS (“post-program survey”). The first survey administered with Cohort 2 participants occurred at study enrollment and served as a control baseline comparison to Cohort 1.

Measures

ACP barriers and facilitators were assessed with 16 yes/no questions (8 barriers and 8 facilitators) derived from qualitative data regarding ACP and developed during the original MY WAY clinical trial, but never published.

ACP readiness and self-efficacy were captured with the 9-item ACP Engagement Survey Process Measures identified from Behavioral Change Theory. The 6-item readiness and

the 3-item self-efficacy subscales have 5-point, Likert responses of “not at all, a little, somewhat, fairly, extremely.” In a field test of these subscales, they demonstrated good reliability and discriminant validity (Sudore et al., 2017; 2013).

For **ACP completion**, participants were asked if they had a legal advance directive. To confirm self-reports post-program, project staff documented whether the participant’s advance directive was notarized after SS and compared this to notary records. All sources of the participant’s advance directive completion measure were combined into a single binary variable (yes/no).

Interview-administered intervention and control baseline surveys also included self-reported demographic characteristics of age (in years), gender (male or female), marital status (married or not married), Tribal affiliation (member, first descendent, family of a member, member of another Tribe), education (on a scale of 1 = less than high school education to 5 = graduate degree), self-rated health (on a scale of 1 = very poor to 6 = excellent), and self-reported diagnosis of any chronic conditions. Chronic conditions included chronic obstructive pulmonary disease, history of stroke, history of heart attack, cancer, chronic kidney disease, type 2 diabetes, heart disease, high cholesterol, and chronic pain.

Analyses

All analyses were conducted in IBM SPSS Statistical Software (27) or Microsoft Excel. We examined participant demographic characteristics using descriptive statistics and stratified analyses. To determine if there were demographic or other differences between the cohorts, we conducted crosstabulation analyses with Bonferroni correction applied. To compare intervention baseline and post-program levels of barriers and facilitators, as well as analyze change over time in ACP readiness, self-efficacy, and completion, we combined the cohorts. As barriers and

facilitators were asked as simple “yes/no” questions, the number of barriers and facilitators listed by participants was calculated before and after the intervention for comparison.

Before combining the individual readiness and self-efficacy items, we ran selectivity and reliability analyses. To check for differences in the sample due to attrition, we computed Little's missing completely at random (MCAR) test. We then conducted crosstabulations again to look for relationships between demographic characteristics and ACP readiness, self-efficacy, and completion measures at intervention baseline. With our combined sample, we conducted a 3 (readiness, self-efficacy, and completion) x 2 (pretest to 8-week posttest) way repeated measures analysis of variance (ANOVA) with demographic characteristics found to be related to intervention baseline measures as between-subjects variables. For 6-month follow-up surveys with Cohort 1, we conducted a separate one-way ANOVA (intervention baseline, post-program, follow-up) for ACP readiness and self-efficacy. We tested the hypothesis that Cohort 2 participants did not change ACP-related readiness and self-efficacy from control baseline to intervention baseline by conducting a third separate one-way repeated measures ANOVA. We also calculated difference scores from control baseline to intervention baseline among Cohort 2 participants and intervention baseline to post-program among all participants.

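### The design is described as waitlist-controlled, but no stated analysis tests Cohort 1's change in outcomes against Cohort 2's change while waiting

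*Combined protocol and SAP*

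**What the plan says.** The Study Design section calls the study quasi-experimental and waitlist-controlled. It gives the reason for two cohorts: "This design split our total participant pool into two cohorts to allow for a comparison group". It then reports that "Results from Cohort 1 were then compared to the waitlisted cohort, or Cohort 2", the latter having waited more than three months on average. The hypothesis itself is worded as change within participants: "after participating in the tailored MY WAY intervention, participants would experience decreased ACP barriers and increased ACP facilitators, readiness, self-efficacy, and completion".

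The Data Collection section adds: "The first survey administered with Cohort 2 participants occurred at study enrollment and served as a control baseline comparison to Cohort 1". Cohort 1's post-program survey came "8-9-weeks after the CIS at posttest". Cohort 2's two pre-programme surveys are separated by "an average of 13 weeks immediately before CIS attendance", read here as the length of the wait.

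The Analyses section combines the cohorts to study change in all five outcomes. The between-subjects variables named for the ANOVA are demographic characteristics related to the baseline measures; cohort is not named. Separate ANOVAs are run within Cohort 1 (to six months) and within Cohort 2 (the waiting period). Difference scores are calculated for Cohort 2's wait and for everyone's intervention period.

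**The concern.** A waitlist cohort is there to show what happens over a similar period without the programme. A pooled before-and-after analysis cannot separate the programme's effect from other change between surveys, such as the effect of being interviewed repeatedly about advance care planning. The waiting period could supply that separation, but only if its change is set directly against change under the programme.

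The plan instead has two separate within-group results: a pooled change, and a test of no change in Cohort 2 while waiting. One significant and one non-significant result do not show that the two changes differ. For barriers, facilitators and completion, no control-period test is stated. A reader of the Study Design section would expect a controlled estimate and would take uncontrolled pre-post results for one.

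**Working it through.** **Step 1: look for a between-cohort test of change.** Each relevant analysis in the Analyses section:

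| Analysis | Who is compared | Tests Cohort 1 change against Cohort 2 waiting change? |
|---|---|---|
| Crosstabulations, Bonferroni corrected | Cohort 1 v Cohort 2, demographic or other differences | No; no outcome change is named |
| Barrier and facilitator counts | Before v after, cohorts combined | No; no test is named |
| 3 x 2 repeated measures ANOVA (readiness, self-efficacy, completion) | Pre v post, cohorts combined | No; the named factors are demographic |
| One-way ANOVA, three time points | Cohort 1 only | No |
| One-way repeated measures ANOVA, waiting period | Cohort 2 only, readiness and self-efficacy | No |
| Difference scores | Cohort 2 waiting, and all participants in the intervention period | No; the second set includes Cohort 2 and no test is stated |

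None of the six is the comparison announced in the Study Design section. The finding rests on this step alone.

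**Step 2: illustrate the consequence.** The plan gives no cohort sizes, SDs or power calculation, so there is no stated figure to reproduce. Assumptions: the 70 people in Aim 3 split 35/35; one continuous outcome; SD of change 1; correlation 0.5 between any two surveys of one person; no programme effect; two-sided 5% tests; paired t-tests standing in for the ANOVAs. Background drift is 0.3 SD of change, in two forms:

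- Equal: 0.3 in every interval.
- Proportional to weeks: 0.3 over Cohort 1's 8.5 weeks, so 0.3 × 13/8.5 = 0.46 over the wait and 0.3 × 12/8.5 = 0.42 over Cohort 2's 12-week intervention period.

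Normal approximation for equal drift: pooled power is Φ(0.3√70 − 1.96) = Φ(0.55) = 0.71, and waiting-period power is Φ(0.3√35 − 1.96) = Φ(−0.19) = 0.43. If the two tests were independent, pooled significant with waiting period not significant would have probability 0.71 × 0.57 = 0.41. They are not independent, because Cohort 2's intervention baseline enters both changes. Simulation (40,000 trials per setting) allows for this:

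| Share of trials | Equal drift | Proportional drift |
|---|---|---|
| Pooled test significant | 70% | 85% |
| Waiting-period test significant | 40% | 75% |
| Pooled significant, waiting period not | 46% | 23% |
| Direct unadjusted contrast significant | 5% | 10% |

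Under proportional drift the direct contrast exceeds 5% because the wait is longer than Cohort 1's interval. The expected difference is 0.30 − 0.46 = −0.16, so these rejections are mostly against the programme.

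**Step 3: precision.** Detectable difference at 80% power, from (1.96 + 0.84) × √(1/n1 + 1/n2):

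- Direct contrast, 35/35: 2.80 × √(2/35) = 0.67, or 0.68 with the t distribution.
- Pooled test, 70 people: 2.80/√70 = 0.33, or 0.34 with the t distribution.

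The waiting-period test with 35 people has a 95% confidence half-width of 2.03/√35 = 0.34 SD. That equals the change the pooled test is able to detect, and its power at that size is about 50%.

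**The case against.** The strongest reply is that the hypothesis is pre-post, the aim is preliminary, the design is declared quasi-experimental, and the waiting-period ANOVA is itself the control. Much of this stands. The pooled analysis does answer the hypothesis as worded. The waiting-period ANOVA is a real safeguard: in the illustration it flags the drift in about 40% of trials, or 75% when drift follows elapsed weeks. Citing 70% or 85% as the rate at which readers would be misled ignores it; 46% and 23% are the fairer figures. Even so, that ANOVA covers two of the five outcomes, and it does not test whether change under the programme exceeds change while waiting.

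Three stronger readings are tempting, and the documents do not support them:

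- That barriers, facilitators and completion have no control-period result at all. The difference scores name no outcomes, so they may include these. What is missing is a stated test.
- That the Data Collection section also promises a contrast of change. Its sentence may mean only a comparison at baseline, which the crosstabulations could serve. The mismatch rests mainly on the Study Design section.
- That no between-cohort test was ever run. The text shows only that none is stated.

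For completion the concern is weaker, since directives notarized after the Sharing Session are tied more closely to the programme.

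**Conclusion.** The point holds as an inconsistency between the stated design and the stated analysis: the comparison for which the waitlist cohort exists has no stated test for any outcome. This follows from the text and needs no numerical assumption.

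The size of any resulting error is unknown. The illustrative figures depend on an assumed 35/35 split, an assumed drift and a single continuous outcome, so they show the mechanism and are not an estimate for this study. Nor would a direct contrast fully isolate the programme's effect, because allocation is not described as random and the two intervals differ in length.

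**What to change.** - For each outcome measured at both Cohort 2 baseline surveys, add one contrast: Cohort 1 change from intervention baseline to post-program, against Cohort 2 change from control baseline to intervention baseline. Adjust for the baseline outcome and give an estimate with a 95% confidence interval. Label it post hoc and preliminary, because the analyses are already reported in the past tense.
- State which outcomes each survey contained. The Measures section suggests, but does not confirm, that both baseline surveys held the planning measures.
- State that allocation is not described as random and that the intervals are 8-9 and about 13 weeks. Add a time-scaled sensitivity analysis.
- For completion, use self-report in both groups if it was kept separately. Verification is described only after the programme ("To confirm self-reports post-program, project staff documented whether" a directive was notarized), and all sources were then merged into one variable. If self-report was not kept, say so.
- Label the pooled pre-post analysis uncontrolled. Where the contrast cannot be done, reword the Study Design section so that it claims no cohort comparison for that outcome.

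The cost is a re-analysis of existing data and lower precision: about 0.68 SD of change detectable at an assumed 35/35, against about 0.34 for the pooled test. Baseline adjustment recovers part of this: at a correlation of 0.5, 0.68 × √(1 − 0.25) = 0.59 if the cohorts start level. Rewording costs nothing but leaves the result uncontrolled.

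### The post-session ANOVAs have no term for the Community Information Session, which appears to be group-delivered, so their standard errors may be too small

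*Combined protocol and SAP*

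**What the plan says.** The Intervention section gives two steps: "The intervention consisted of two steps: attendance at a Community Information Session (CIS) and attendance at an individual Sharing Session (SS". It does not say how many Community Information Sessions (CIS) were held, how many people came to each, or how they were run. The Recruitment section adds that interested people could meet staff at a CIS and then be screened and enrolled.

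Under Analyses, the main model is stated as "With our combined sample, we conducted a 3 (readiness, self-efficacy, and completion) x 2 (pretest to 8-week posttest) way repeated measures analysis of variance (ANOVA"). Its only between-subjects factors are demographic ones, chosen because they were associated with the outcomes before the intervention. For longer follow-up of Cohort 1, "we conducted a separate one-way ANOVA (intervention baseline, post-program, follow-up) for ACP readiness and self-efficacy". A third ANOVA covers the Cohort 2 waiting period. None of these includes a session effect, a cluster-robust standard error or an ICC.

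On possible household links, eligibility extends to any "enrolled Tribal member, spouse of a Tribal member, first descendant, or a member of another AIAN Tribe". The documents do not say whether both members of any couple enrolled, and they list no household identifier.

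**The concern.** A repeated measures ANOVA deals with the correlation between one person's before and after scores. It assumes that different people's changes are independent. Attenders at one CIS would plausibly share a presenter, a discussion and a date. If one session goes unusually well or badly, or draws an unusual group, its attenders' changes move together.

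The main estimate is a mean change over both cohorts, so session-to-session variation in change enters it directly but is missing from its error term. The same holds for the Cohort 1 contrasts out to 6 months. The study is described as feasibility work with preliminary outcomes, but the Study Design section also states a hypothesis to be tested, so the error rate of the tests and the width of the intervals matter.

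**Working it through.** The plan states no power, alpha, effect size or standard deviation, so there is no figure of its own to reproduce.

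**Input from the documents**
- Target sample: 70 (Study Aims: "Examine the preliminary outcomes of the culturally tailored MY WAY ACP curriculum guide with 70 tribal members").

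**Assumed inputs, because the documents give none**
- m, analysed attenders per session: 5 to 10. If all 70 are analysed, this means 70/10 = 7 to 70/5 = 14 sessions.
- ICC of the change score within a session: 0.01 to 0.10. Only correlation of change matters here, since stable differences between people cancel from a within-person change.
- Two-sided 5% tests.

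**Formulas for the mean change**
- Design effect: DE = 1 + (m − 1) × ICC
- True SE divided by reported SE: √DE
- Effective sample size: 70 / DE
- Actual two-sided error of a nominal 5% test: 2 × [1 − Φ(1.96 / √DE)]

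**Results**

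| m | ICC | DE | SE ratio | Effective N | Actual error |
|---|---|---|---|---|---|
| any | 0 | 1 | 1.00 | 70 | 5.0% |
| 5 | 0.01 | 1 + 4 × 0.01 = 1.04 | 1.02 | 67.3 | 5.5% |
| 5 | 0.05 | 1 + 4 × 0.05 = 1.20 | 1.10 | 58.3 | 7.4% |
| 5 | 0.10 | 1 + 4 × 0.10 = 1.40 | 1.18 | 50.0 | 9.8% |
| 10 | 0.01 | 1 + 9 × 0.01 = 1.09 | 1.04 | 64.2 | 6.0% |
| 10 | 0.05 | 1 + 9 × 0.05 = 1.45 | 1.20 | 48.3 | 10.4% |
| 10 | 0.10 | 1 + 9 × 0.10 = 1.90 | 1.38 | 36.8 | 15.5% |

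Outside the assumed range of session sizes, m = 3 with ICC 0.01 gives DE 1.02 and 5.2% error, and m = 14 with ICC 0.10 gives DE 2.30 and 19.6%.

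**Couples.** If a share f of participants enrolled as couples, with correlation ρ of change within a couple, DE = 1 + f × ρ. For assumed f = 0.1 to 0.4 and ρ = 0.1 to 0.5, DE runs from 1 + 0.1 × 0.1 = 1.01 to 1 + 0.4 × 0.5 = 1.20, and the error from 5.1% to 7.4%.

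**Which analyses are exposed.** The combined baseline-to-post-program ANOVA and the Cohort 1 6-month ANOVA both span the CIS. The Cohort 2 waiting-period ANOVA compares two surveys that both come before the CIS, so shared delivery cannot cluster it. The barrier and facilitator counts and the difference scores are calculated with no test or standard error named, so there is no error term to fault.

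**The case against.** The strongest reply is that the premise is inferred. The documents never state that a CIS was held for a group, and they give no session size, count or correlation. A reader might conclude that the reported standard errors and p-values are too small throughout. The documents do not support that: correlated change is plausible but not shown, and the low end of the range is trivial. What stands is that group delivery is the natural reading of a community session set against an individual one, at which people could also meet staff before enrolling.

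A second reply concerns the false-positive rates. If the CIS changes nobody, shared delivery alone creates no correlation of change. An inflated error rate then needs sessions whose effects differ but average to zero, or clustering that comes from who attended together or when. This is correct and limits the 5.5% to 15.5% figures. It does not touch the standard error: wherever change varies by session, intervals that ignore session are too narrow. The survey 8 to 9 weeks (Cohort 1) or about 12 weeks (Cohort 2) after the CIS, and the individual session, may also dilute a session effect.

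A third reply is that the couples argument is thin. A spouse qualifies without the Tribal member enrolling, and no enrolled couple is documented. A reader might infer that couples are clustered in the data, but the eligibility rule shows only that they could be.

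Last, with few sessions, random session and household variances may be barely estimable, and a linear mixed model does not suit the yes/no completion outcome. This stands. It argues for a simpler method used as a sensitivity analysis, but not for leaving the check out.

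**Conclusion.** The point holds for two analyses: the combined-cohort baseline-to-post-program ANOVA and the Cohort 1 6-month ANOVA. Neither allows for session, and the apparent delivery format makes independence doubtful. Their standard errors may be too small, by a factor of 1.02 to 1.38 under the assumptions above (1.20 at 10 per session and ICC 0.05). The effect therefore runs from negligible to moderate, and there is none if changes are uncorrelated within sessions. It should not be read as a defect of every outcome analysis or as proof that any result is a false positive. The preliminary character of the study lowers the weight of the point but does not remove it, because hypothesis tests are run.

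**What to change.** Give each participant a CIS session ID. The Data Collection section ties the intervention baseline survey to the CIS, so session should be recoverable from dates. For Cohort 2 the timing is worded less clearly, so the CIS date itself is the safer key. Report the number of sessions and their sizes, by cohort.

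Alongside the planned ANOVAs, report the baseline-to-post-program and Cohort 1 6-month contrasts with an analysis that allows for session, labelled as a sensitivity analysis. For readiness and self-efficacy, use cluster-robust standard errors with a small-sample correction, or a test on session-mean changes. For completion, which enters only the baseline-to-post-program analysis, use a method suited to a binary outcome, such as a logistic model with session-robust standard errors. Add household clustering only if enrolled couples can be identified from existing records. The Cohort 2 waiting-period test needs no session term.

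The cost is one added variable and a small amount of extra analysis, with no further contact with participants if the dates were kept. The downside is somewhat wider intervals and limited precision if there are few sessions: at 7 to 14 sessions, a test on session means has only 6 to 13 degrees of freedom.

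### Advance directive completion is ascertained differently before and after the program, so its before-after change mixes real change with a change in measurement, in a direction the documents do not settle

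*Combined protocol and SAP*

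**What the plan says.** The ACP completion paragraph under Measures gives one source that is not tied to a time point: "participants were asked if they had a legal advance directive". The next sentence adds further sources at one time only. It opens "To confirm self-reports post-program, project staff documented whether the" and continues that the participant's "advance directive was notarized after SS and compared this to notary records". The paragraph ends by saying that all sources of the participant's "advance directive completion measure were combined into a single binary variable (yes/no"). It does not say whether any positive source was enough, whether sources had to agree, or whether a record overrode a self-report.

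Under Analyses, completion is part of a "3 (readiness, self-efficacy, and completion) x 2 (pretest to 8-week posttest) way repeated measures analysis of variance (ANOVA") in the combined cohorts. The separate test over the waiting period concerns whether "Cohort 2 participants did not change ACP-related readiness and self-efficacy from control baseline to intervention baseline", so completion is not named there. Difference scores over the wait are mentioned without naming outcomes. Neither section describes a staff or notary check at the control baseline or the intervention baseline.

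**The concern.** A before-after comparison needs the same yardstick at both ends. Here a second and third source appear at the time the intervention has been delivered, and they feed the same binary variable. Any effect of adding those sources is counted as part of the change in completion, and the repeated measures analysis cannot separate the two.

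Completion is one of the outcomes named in the study hypothesis, and the only one for which an external check is described. The wait in Cohort 2 does not help. Both of its surveys precede the program, so a check limited to post-program does not reach them. Any comparison over the wait would set self-report against self-report and could not show the effect of the added sources.

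**Working it through.** The documents give no completion rate, no accuracy of self-report and no sample-size calculation, so there is no stated figure to reproduce. The calculation shows only which way the artefact can go, and how far, on assumed inputs.

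**From the documents.** Self-report is the only source described for baseline. Staff and notary sources are added post-program. The combination rule is not stated. The planned number is 70 (Study Aims).

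**Assumed.** True prevalence is 0.20 at baseline (p0) and p1 after the program. Self-report has sensitivity Se and specificity Sp. Records find a directive with sensitivity r = 0.7 to 1.0, give no false positives, and err independently of self-report.

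**Formulas.**
- Baseline, self-report: p0·Se + (1 - p0)(1 - Sp)
- Post, any positive source: p1·[1 - (1 - Se)(1 - r)] + (1 - p1)(1 - Sp)
- Post, sources must agree: p1·Se·r
- Post, record overrides: p1·r

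**No true change (p0 = p1 = 0.20).** Observed change in percentage points; each range runs over r from 0.7 to 1.0:

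| Se, Sp | Baseline observed | Self-report both times | Any source | Agreement | Record overrides |
|---|---|---|---|---|---|
| 0.80, 1.00 | 0.16 | 0 | +2.8 to +4.0 | -4.8 to 0 | -2.0 to +4.0 |
| 0.90, 0.95 | 0.22 | 0 | +1.4 to +2.0 | -9.4 to -4.0 | -8.0 to -2.0 |
| 0.95, 0.85 | 0.31 | 0 | +0.7 to +1.0 | -17.7 to -12.0 | -17.0 to -11.0 |
| 1.00, 0.90 | 0.28 | 0 | 0 | -14.0 to -8.0 | -14.0 to -8.0 |

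The two extremes in full:
- Any source, Se 0.80, Sp 1.00, r 1.0: 0.20 × [1 - 0.20 × 0] - 0.16 = +0.040, or 0.040 × 70 = 2.8 people.
- Agreement, Se 0.95, Sp 0.85, r 0.7: 0.20 × 0.95 × 0.7 - 0.31 = 0.133 - 0.31 = -0.177, or 0.177 × 70 = 12.4 people.

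**True rise of 40 points (0.20 to 0.60, assumed).** Self-report at both times shows 32 to 36 points. Any source shows 34.1 to 44.0, agreement 8.9 to 32.0, and record overrides 11.0 to 44.0. Compared with self-report at both times, the any-source rule is equal or higher and the agreement rule is equal or lower.

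**If records show only notarizations after the Sharing Session.** The formulas above let records reveal older directives too. Suppose instead that they detect every new notarization and no old directive, with Se 0.80 and Sp 1.00. Baseline is 0.20 × 0.80 = 0.16. The any-source post-program rate is 0.16 + 0.40 = 0.56, so the observed rise is 40 points, which is the truth. Self-report at both times gives 0.60 × 0.80 - 0.16 = 32. With no true change, the any-source artefact is 0. Under strict agreement on this reading, older directives would all drop out and the shift would be minus the whole observed baseline rate. The -17.7 to +4.0 range is therefore an illustration and not a bound.

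**The case against.** A reader might infer that the rise in completion is biased upward, because an older directive missed at baseline can surface only afterwards. With assumed prevalences of 25% to 35% and self-report sensitivities of 80% to 95%, the shortcut p0 × (1 - Se) would then give 0.25 × 0.05 = 1.25 points up to 0.35 × 0.20 = 7 points. The case against that reading is strong:

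- The event staff documented is notarization after the Sharing Session. That is a genuine new completion, and nothing says staff searched for earlier directives.
- The stated purpose is to confirm self-reports. If unconfirmed reports were turned into *no*, the change moves downward.
- The shortcut assumes an any-source rule, records that find every old unreported directive, and no false positive self-reports. The documents support none of these.
- The plan does not claim that the Cohort 2 wait corrects completion, so it cannot be faulted for a correction that fails.
- Self-report alone at baseline is inferred from silence. Nothing shows that the notary records cover earlier dates or directives notarized elsewhere.

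All of this stands against an upward-bias claim and against that magnitude. It does not remove the narrower point. The added check is explicitly limited to post-program, the merged variable is analysed before against after, and no other passage makes the two ends comparable. An unstated rule that can move the result either way is more than a missing detail.

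**Conclusion.** The point holds in a limited form. As described, completion is measured by self-report at the intervention baseline and by self-report combined with staff and notary information after the program. The before-after change therefore contains an unknown measurement component. The documents do not fix its sign: zero or upward if any positive source counts and records can reveal older directives, downward if unconfirmed self-reports are recoded to *no*.

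Any size is an assumption. With no true change, 20% baseline prevalence and the accuracy ranges in the table, it runs from about -18 to +4 points according to the rule. The documents report no completion result, so nothing can be said about how far a published figure is affected. This should be corrected because the remedy is cheap and it changes what the completion result can support.

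**What to change.** 1. Report completion by self-report alone at every time point where the question was asked, as the like-for-like analysis, beside the merged variable.
2. Report separately, as dated new events, the directives notarized after the intervention baseline survey.
3. State how the sources were combined and how discordant ones were resolved, and show the post-program cross-tabulation of self-report against records.
4. Where the notary records already consulted reach back far enough, apply the same look-up to dates before the Community Information Session. The first three steps should not wait on this.

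The cost is a little more analysis: self-report was already collected and the records were already consulted. Self-report alone may under-count true new completions (32 points against a true 40 in the example above), which is why the dated count belongs beside it. The reported change in completion may become less favourable.
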